## Introduction

This Statistical Analysis Plan (SAP) outlines the statistical methods and procedures to be used for analyzing data from the study evaluating the value of heart-lung interactions in predicting the hemodynamic response to the Open Lung Approach (OLA).

## Study Objectives

### *Primary Objective*

To evaluate capacity of baseline heart-lung interaction variables (Changes in Pulse pressure variation -PPV- with Tidal Volume Challenge -TVC-) in predicting the decrease in CI following the OLA approach (recruitment maneuver-RM- with individualized Positive End-Expiratory Pressure -PEEP-), by comparing baseline CI and CI 5 minutes post-MR. A clinically significant decrease in CI is defined as at least 10%

### *Secondary Objectives*

- To evaluate the capacity of other heart-lung interaction variables (TVC, SVV, and PPV) in predicting a  $\geq 10\%$  decrease in CI at 1, 5, and 15 minutes after performing recruitment maneuver with individualized PEEP (OLA).
- To describe the correlation between changes in CI and MAP pre- and post-MR.
- To describe the effect of individualized PEEP on hemodynamic parameters obtained through minimally invasive monitoring using the PRAM method continuously during the first 15 minutes after MR with individualized PEEP, compared to baseline values of: indexed stroke volume (SVI), cardiac index (CI), pulse pressure variation (PPV), dynamic arterial elastance (EaDyn), and cardiovascular system impedance (Ztotal).

## Study Design

## Prospective observational cohort study

### Study Population

#### *Inclusion Criteria*

Patients aged over 18 years undergoing scheduled non-cardiothoracic surgery; under controlled invasive mechanical ventilation with invasive arterial monitoring; in the supine position; with a positive air test or clinical indication for recruitment maneuver.

#### *Exclusion criteria:*

Chronic pulmonary disease (defined as chronic obstructive pulmonary disease grade 3 or higher, or any condition requiring long-term oxygen therapy); congenital cardiac malformations; severe valvulopathy; NYHA (New York Heart Association) grade III/IV heart failure; arrhythmias; history of decreased ventricular systolic function (Left Ventricular Ejection Fraction -LVEF- <40% or Tricuspid Annular Plane Systolic Excursion -TAPSE- <17 cm/s); history of pulmonary hypertension; Body Mass Index -BMI- >35 (due to altered pulmonary and thoracic compliance); heart rate to respiratory rate ratio <3.6; presence of inspiratory efforts; open chest; increased intra-abdominal pressure (due to pathology or pneumoperitoneum); altered pulmonary or thoracic compliance due to surgery (Trendelenburg or reverse Trendelenburg position); uncorrected arterial waveforms (resonant or damped); and any contraindication to performing lung recruitment maneuvers. These contraindications include: pulmonary emphysema, pulmonary bullae, uncontrolled hemodynamic instability, right heart failure, elevated intracranial pressure (due to reduced jugular vein return flow) or absence of monitoring when necessary, bronchospasm, and undrained pneumothorax.

### Endpoints

#### *Primary*

To evaluate the ability of changes in PPV with TVC to predict a ≥10% decrease in CI at 5 minutes post-OLA.

#### *Secondary*

- To evaluate the ability of TVC, PPV, and SVV to predict a ≥10% decrease in CI at different time points (1, 5, and 15 minutes).
- To assess the correlation between MAP and CI to monitor the hemodynamic impact of the OLA.
- To evaluate the hemodynamic impact of the OLA using various parameters obtained with the PRAM method continuously during the first 15 minutes

after RM with individualized PEEP, compared to baseline values of: indexed stroke volume (SVI), cardiac index (CI), pulse pressure variation (PPV), dynamic arterial elastance (EaDyn), and cardiovascular system impedance (Ztotal).

## **Randomization and Blinding**

This study does not involve randomization as it is observational. Blinding is not applicable.

## **Sample Size and Power Calculations**

Based on data from a pilot study with 6 patients, which reported an effect size (Cohen's d) of 0.7, a sample size of 66 patients was calculated to provide 80% power, ensuring the detection of a significant difference, if present, with a significance level ( $\alpha$ ) of 0.05. To account for an expected dropout rate of 10%, a recruitment target of 72 patients was set. This sample size also allows for the estimation of an area under the curve (AUC) of 0.75 for the ROC curve of the logistic regression model, demonstrating good discriminative ability with a precision of  $\pm 0.065$ .

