## **Statistical Methods**

A statistical analysis of the results obtained from the data collection sheet will be conducted. This document includes the following hemodynamic and ventilatory variables:

- At baseline, after the tidal volume challenge, 1 minute after the recruitment maneuver, and 5 minutes after the recruitment maneuver: driving pressure, PEEP, mean airway pressure, respiratory rate, oxygen saturation by pulse oximetry, and the result of the tidal volume challenge.
- At baseline, after the tidal volume challenge, and every minute for 15 minutes after the recruitment maneuver: MAP, CI, SVI, heart rate, Ztotal, EaDyn, PPV, and SVV.

1. Ability of TVC, PPV, and SVV to predict a  $\geq 10\%$  decrease in CI following OLA (at 1, 5, and 15 minutes): Evaluation of the predictive value of heart-lung interaction variables for hemodynamic tolerance to MR, defined as a  $\geq 10\%$  decrease in CI. Logistic regression models will be developed using the following predictors: change in PPV with TVC, the categorical outcome of TVC, SVV with a  $V_T$  of  $6 \text{ mL}\cdot\text{kg}^{-1}$  ( $SVV_6$ ), SVV with a  $V_T$  of  $8 \text{ mL}\cdot\text{kg}^{-1}$  ( $SVV_8$ ), PPV with a  $V_T$  of  $8 \text{ mL}\cdot\text{kg}^{-1}$  ( $PPV_8$ ), and PPV with a  $V_T$  of  $6 \text{ mL}\cdot\text{kg}^{-1}$  ( $PPV_6$ ). The binary outcome will be a  $\geq 10\%$  decrease in CI. The model's performance will be evaluated using sensitivity, specificity, and predictive values. ROC curves and the AUC will be calculated to compare the predictive power of TVC,  $SVV_6$ ,  $SVV_8$   $PPV_6$  y  $PPV_8$ .
2. A Pearson correlation will be performed to evaluate the relationship between changes in CI and changes in MAP.
3. The hemodynamic consequences of MR with individualized PEEP will be described using repeated measures of CI, SVI,  $dP/dt_{MAX}$ , EaDyn, and  $Z_{total}$ .

All analyses will be conducted in R (version 4.4.1).

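### 72 recruits less 10% dropout leave 64 to 65 patients, not 66, and the 80% power depends on a group split that the plan neither states nor controls

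*SAP*

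**What the plan says.** The Sample Size and Power Calculations section starts from a Cohen's d of 0.7 ("Based on data from a pilot study with 6 patients") and a significance level of 0.05. It concludes that "a sample size of 66 patients was calculated to provide 80% power, ensuring the detection of a significant difference, if present". It then adds: "To account for an expected dropout rate of 10%, a recruitment target of 72 patients was set". It gives no test, no sidedness and no expected share of patients in any group. The same section offers a second basis for the sample size, the precision of an AUC of 0.75.

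Three other sections bear on the power statement:

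- **Study Design; Randomization and Blinding.** The study is a "Prospective observational cohort study", and "This study does not involve randomization as it is observational".
- **Endpoints, Primary.** The aim is "To evaluate the ability of changes in PPV with TVC to predict a ≥10% decrease in CI at 5 minutes post-OLA".
- **Statistical Methods.** "Logistic regression models will be developed using the following predictors", and the list of predictors includes "the categorical outcome of TVC". ROC curves, a Pearson correlation and repeated-measures description follow. No comparison of two group means is planned.

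**The concern.** There are two separate points.

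First, the recruitment target does not deliver the size it is meant to protect. If 66 is the number needed after dropout, which is how the two sentences read together, then 72 is too few at the stated 10%.

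Second, a Cohen's d and a significant difference suggest a comparison of two means, and the power of such a comparison depends on how the patients divide. Here the division is a result of the study. The groups could be patients with and without a CI decrease of at least 10%, or patients with a positive and a negative TVC. Neither split is set by design and neither is forecast in the SAP. The 80% is nevertheless given without conditions, in wording that promises detection. What is at stake is how far a reader can rely on the stated power; no planned analysis becomes invalid.

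**Working it through.** **Inputs from the SAP.** d = 0.7; alpha = 0.05; power 80%; N = 66; dropout 10%; target 72.

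**Inputs assumed.** Two-sample t-test, two-sided unless noted. The 30% share in step 3 is an illustration.

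**Step 1: reproduce the 66.** For group sizes n1 and n2, the noncentrality is d × √(n1·n2/(n1+n2)) with n1+n2−2 degrees of freedom. At 33/33 this is 0.7 × √16.5 = 2.84 with 64 df, and two-sided power is 0.7997. The exact requirement is 33.02 per group, 66.05 in total. The normal approximation gives 32.04 per group, rounded up to 33. So 66 reproduces.

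Other variants at the same inputs do not give 66: a paired t-test needs 19 patients and a one-sided two-sample test at 1:1 needs 52. A one-sided test with an uneven split does fit: 18/48 gives 0.805. That reading also needs a split, and a sidedness, that the SAP does not state.

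**Step 2: dropout.**

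- Patients left from 72: 72 × (1 − 0.10) = 64.8, so 64 to 65.
- Recruits needed for 66: 66/(1 − 0.10) = 73.3, so 74. Check: 73 × 0.9 = 65.7, which is short; 74 × 0.9 = 66.6, which is enough.
- Likely origin of 72: 66 × 1.1 = 72.6, rounded down. That adds 10% of 66, whereas the loss is 10% of those recruited.
- Two-sided t-test power at an even split: 0.787 at 32/32 and 0.793 at 32/33, against 0.7997 at 33/33. The loss is about 1 point.

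**Step 3: dependence on the split.** Two-sided t-test, d = 0.7, N = 66:

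| Split | Share in smaller group | Power |
|---|---|---|
| 33/33 | 50% | 0.7997 |
| 26/40 | 39% | 0.781 |
| 25/41 | 38% | 0.776 |
| 20/46 | 30% | 0.730 |

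Shares above 50% mirror these. Power is therefore within 2 points of 80% for 26 to 40 patients in one group, that is 26/66 = 39% to 40/66 = 61%.

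All these figures take d = 0.7 as given.

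**The case against.** The strongest reply is that 66 is not wrong: it follows from the stated d, alpha and power under an ordinary calculation. Every power figure is conditional on its assumptions, a protocol may spell them out, and the sample size has a second basis in AUC precision, which belongs to the planned ROC analysis. Much of this stands. A bare request to name the test and contrast would be a request for missing detail and is not the point made here. The AUC rationale means that the 80% is not the sole support for the sample size. It does not make the 80% unconditional, and it does not alter the dropout arithmetic, which is wrong on the SAP's own figures.

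A reader might infer three stronger things, none of which the document supports:

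- **That the study is underpowered.** The SAP gives no expected group share, so nothing in it points to a split outside 39% to 61%. The 0.73 belongs to a share assumed for illustration.
- **That 66 fits only a near-even split.** The SAP states no sidedness, and a one-sided test at about 18/48 also fits.
- **That with 64 to 65 patients no split reaches 80%.** This is true of the two-sided t-test, whose best values are 0.787 and 0.793. A one-sided test at 18/46 gives 0.801.

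It is also fair to say that the promise of detection is loose wording, since the same sentence says 80% power and allows that there may be no difference. Even so, 80% power does not ensure detection under any test.

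**Conclusion.** The point holds as a minor correction.

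The dropout step is wrong without any further assumption: 72 recruits leave 64 to 65 patients, and 74 are needed to keep 66. The cost is two recruits, or about 1 point of power at an even split if a two-sided two-sample t-test was used.

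The 80% is conditional on group shares that the SAP does not state and that an observational cohort cannot fix. How strongly it depends on them rests on the inferred two-sided test. Under that test the loss is at most 2 points across a wide middle range of splits and grows outside it. Which range applies cannot be determined from the document.

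**What to change.** **Dropout sentence.** Either state that 72 recruits leave 64 to 65 patients after 10% dropout, with about 79% power at an even split if the sponsor confirms a two-sided two-sample t-test, or set the target at 74.

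**Power sentence.** Replace the assurance of detection with a conditional statement, for example: Assuming d = 0.7 and group shares of [shares and their basis, sponsor to confirm], 66 evaluable patients give [power] for [test, sidedness and contrast, sponsor to confirm]. Follow it with power across plausible shares for the confirmed test. The t-test figures given here should go into the SAP only if that test is confirmed.

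**Cost.** A few sentences in the SAP and a slightly less favourable stated power, or two more recruits. No larger increase is called for and no planned analysis changes.

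### The ±0.065 precision stated for the AUC is about one standard error; with 66 patients and an AUC of 0.75 the 95% half-width is about ±0.12 or wider

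*SAP*

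**What the plan says.** The section Sample Size and Power Calculations makes two statements about size. The first derives the number from a six-patient pilot, "which reported an effect size (Cohen's d) of 0.7", and concludes that "a sample size of 66 patients was calculated to provide 80% power" at a significance level of 0.05, with 72 to be recruited to allow for dropout. The second says the same size can also deliver "an area under the curve (AUC) of 0.75 for the ROC curve of the logistic regression model, demonstrating good discriminative ability with a precision", and puts that precision at ±0.065.

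The section gives no confidence level for the ±0.065, no formula, and no expected frequency of the outcome that defines the two ROC groups. It does not call the figure a standard error. The outcome itself is set under Primary Objective: "A clinically significant decrease in CI is defined as at least 10"%.

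**The concern.** The precision of an AUC depends on the AUC and on how many patients fall on each side of the outcome. With 66 patients in total, neither group can be large, and ±0.065 looks too tight for a confidence interval.

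The primary objective is to predict a CI decrease of at least 10% from the change in PPV with the tidal volume challenge. Statistical Methods evaluates the predictors by logistic regression, ROC curves and AUC. The ±0.065 is the one planning figure in the SAP expressed on the AUC scale. If it is half the true value, readers will expect the study to place the AUC between 0.685 and 0.815 when it cannot. They may also over-read differences between the AUCs of the several predictors that Statistical Methods sets out to compare.

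**Working it through.** **Inputs from the SAP (Sample Size and Power Calculations).** N = 66 analysable, 72 recruited, AUC A = 0.75, stated precision ±0.065, Cohen's d = 0.7, α = 0.05, power 80%.

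**Assumption.** The frequency of a CI decrease of at least 10% is not given. I use 10% to 80%, with a 33/33 split as a near-best reference case.

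**1. The sample size itself.** A two-sided comparison of two equal groups with d = 0.7, α = 0.05 and 80% power needs 33 per group, so 66 in total. The t-test version gives 33.02 per group. The 66 reproduces, and it implies equal groups.

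**2. The AUC precision at 33/33.** The Hanley-McNeil variance, with n₁ patients with the outcome and n₀ without, is

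Var = [A(1−A) + (n₁−1)(P₁−A²) + (n₀−1)(P₂−A²)] / (n₁n₀), where P₁ = A/(2−A) and P₂ = 2A²/(1+A).

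- P₁ = 0.75/1.25 = 0.600, so P₁−A² = 0.600 − 0.5625 = 0.0375
- P₂ = 1.125/1.75 = 0.6429, so P₂−A² = 0.6429 − 0.5625 = 0.0804
- Var = [0.1875 + 32 × 0.0375 + 32 × 0.0804] / 1089 = 0.00364
- SE = 0.0603, and 1.96 × SE = 0.118

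The expected 95% interval is 0.75 ± 0.118, or 0.632 to 0.868. The stated ±0.065 does not reproduce.

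**3. Other outcome frequencies, N = 66.**

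| With / without outcome | SE | 95% half-width | Ratio to 0.065 |
|---|---|---|---|
| 40 / 26 (60%) | 0.059 | ±0.116 | 1.8 |
| 33 / 33 (50%) | 0.060 | ±0.118 | 1.8 |
| 26 / 40 (40%) | 0.064 | ±0.125 | 1.9 |
| 20 / 46 (30%) | 0.070 | ±0.137 | 2.1 |
| 13 / 53 (20%) | 0.084 | ±0.164 | 2.5 |

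The minimum, ±0.116, falls at about 39 or 40 patients with the outcome. With all 72 recruits analysed, the smallest half-width is still ±0.111.

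**4. Lower confidence levels.** At 33/33 the 90% half-width is ±0.099 and the 80% half-width ±0.077. Neither gives ±0.065.

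**5. Other methods, 95% half-width.**

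- Obuchowski binormal variance: ±0.125 at 33/33.
- Simulation of the empirical AUC under a binormal model, 20,000 runs per split: ±0.117 at 33/33 (central 95% of estimates 0.63 to 0.86), ±0.119 at 26/40 and ±0.127 at 20/46.
- The crude 1.96 × √(A(1−A)/66): ±0.104.

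**6. What ±0.065 corresponds to.** At 33/33 it is 0.065/0.0603 = 1.08 standard errors, which covers about 72%. At 40% outcome frequency it is 1.02 standard errors (69%), and at 30% it is 0.92 (64%). It is therefore about one standard error. The SAP does not show how it was obtained.

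**7. What a 95% half-width of ±0.065 would need.** About 216 patients at 50% outcome frequency, 241 at 40% and 294 at 30%. That is 216/66 = 3.3 to 294/66 = 4.5 times the planned number.

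**The case against.** The strongest reply is that the SAP never calls ±0.065 a 95% interval. As a standard error it is close to exact: 26 patients with the outcome and 40 without give 0.064, and 23 and 43 give 0.067. On that reading the number is right and only its label is missing. This is a fair limit on the claim, but it does not rescue the sentence. A ± figure called the precision of an estimate is normally read as an interval half-width, and nothing in the text tells the reader otherwise. If a standard error was meant, the sentence still has to say so and give the interval that follows.

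The phrase about good discriminative ability may describe an AUC of 0.75 and not promise a lower confidence limit. The SAP sets no threshold for good, and an interval of about 0.63 to 0.87 still excludes 0.5. That reading is possible. Even so, 0.75 is a planning assumption here, and a sample size cannot demonstrate it.

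Finally, the ±0.065 did not set the sample size and no analysis or decision rule uses it. The reported AUC and its interval will come from the data. This stands: the error misstates what the study can deliver, but it does not bias an analysis.

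**Conclusion.** The concern holds. Read as a 95% half-width, ±0.065 is wrong by a factor of 1.8 to 2.1 for outcome frequencies from 30% to 70%, and by more if the outcome is rarer. With 66 patients and a true AUC of 0.75, the expected 95% half-width is about ±0.12 near a 50% frequency and about ±0.14 at 30%.

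This rests on the SAP's own AUC and N, and on the ordinary reading of ± as a confidence half-width. The outcome frequency is assumed, but no frequency tried, at N = 66 or 72 and at 80%, 90% or 95% confidence, gives ±0.065. The derivation of 66 from d = 0.7 is arithmetically sound for equal groups and is not in question here.

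**What to change.** In Sample Size and Power Calculations, replace the sentence on the AUC with wording such as:

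> With 66 evaluable patients and a true AUC of 0.75, the expected 95% confidence interval half-width (Hanley-McNeil) is about ±0.12 if 50% of patients have a CI decrease of at least 10%, and about ±0.14 if 30% do.

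State the outcome frequency that the investigators expect, and delete the claim that good discriminative ability will be demonstrated.

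The cost is one sentence. The sample size, endpoints and analyses stay as they are; the stated precision becomes less favourable.

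### With 66 patients an AUC of 0.75 has a 95% half-width of about 0.12 to 0.14, not the stated 0.065, and the 0.75 has no source and is not reconciled with the pilot d of 0.7

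*SAP*

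**What the plan says.** Everything at issue is in one paragraph of the SAP, Sample Size and Power Calculations. The basis for the sample size is a small pilot: "Based on data from a pilot study with 6 patients, which reported an effect size" of 0.7 on Cohen's scale. From this, "a sample size of 66 patients was calculated to provide 80% power" at a significance level of 0.05. The variable and the groups behind d are not named, and neither is the sidedness of the test.

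The paragraph then adds that the same number of patients permits estimation of "an area under the curve (AUC) of 0.75 for the ROC curve of the logistic regression model, demonstrating good discriminative ability", and gives the precision as ±0.065. It does not say whether ±0.065 is a standard error or a confidence half-width, at what confidence level, or for what number of events. It gives no source for 0.75.

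The primary endpoint concerns one predictor: "To evaluate the ability of changes in PPV with TVC to predict" a fall in CI of at least 10% at 5 minutes. Statistical Methods lists six predictors for logistic regression models and does not say whether they enter singly or jointly.

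**The concern.** The primary question is how well a variable predicts a binary outcome, so the width of the interval around the AUC is the design property that matters most. A reader who takes ±0.065 as a 95% half-width expects an interval of about 0.685 to 0.815 around an AUC of 0.75. If the real interval is about twice as wide, the study may be unable to separate moderate from weak discrimination, and the plan gives no warning of this.

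The paragraph also uses two planning values, d = 0.7 for power and AUC 0.75 for precision, without saying how they relate. A standardised difference between two outcome groups translates into an AUC under simple assumptions, so the two can be compared.

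**Working it through.** **Inputs from the SAP:** d = 0.7; power 80%; α = 0.05; N = 66; AUC = 0.75; precision ±0.065. **Assumed, because the SAP does not give it:** the number of patients with the CI decrease. I use 33/33, the most favourable split, and 20/46.

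**1. The plan's N.** Two equal groups, two-sided normal formula: n per group = 2(1.960 + 0.842)²/0.7² = 32.04, rounded up to 33, so N = 66. This reproduces the stated figure. (The t-test power at 33/33 is 0.7997.) The plain reading is therefore a comparison of two groups. In a single cohort the natural two groups are patients with and without the CI decrease.

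**2. Precision at AUC 0.75.** Hanley-McNeil, with n₁ events and n₂ non-events:

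SE² = [A(1−A) + (n₁−1)(Q₁−A²) + (n₂−1)(Q₂−A²)] / (n₁n₂), where Q₁ = A/(2−A) and Q₂ = 2A²/(1+A).

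For A = 0.75: Q₁ = 0.6000, Q₂ = 0.6429, A² = 0.5625, A(1−A) = 0.1875.

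- 33/33: (0.1875 + 32×0.0375 + 32×0.0804)/1089 = 3.959/1089, so SE = 0.0603 and 1.96×SE = 0.118.
- 20/46: (0.1875 + 19×0.0375 + 45×0.0804)/920 = 4.516/920, so SE = 0.0701 and 1.96×SE = 0.137.

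The stated 0.065 lies between these two standard errors. As a half-width at 33/33 it equals 0.065/0.0603 = 1.08 standard errors, which is about 72% confidence. An 80% interval at 33/33 already has half-width 1.282×0.0603 = 0.077. If all 72 recruited patients were analysed and split evenly, the 95% half-width would be 0.113.

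**3. N needed for a 95% half-width of 0.065.** Increasing N in the same formula at AUC 0.75 and 50:50, the half-width first falls to 0.065 at N = 216 (108/108).

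**4. Relation of d to AUC.** For one normally distributed predictor with equal variances in the two outcome groups, AUC = Φ(d/√2).

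- d = 0.7: Φ(0.495) = 0.690.
- AUC 0.75: d = √2 × Φ⁻¹(0.75) = 0.954, which is 0.954/0.7 = 1.36 times the pilot value.

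**5. Precision at AUC 0.69**, same formula:

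| Split | SE | 95% half-width |
|---|---|---|
| 33/33 | 0.0652 | 0.128 |
| 20/46 | 0.0745 | 0.146 |

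At 33/33 the expected interval runs from about 0.56 to 0.82.

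**The case against.** The SAP never calls ±0.065 a 95% half-width. If it was meant as a standard error, the value is about right. That stands as a possible explanation, but an unlabelled ± after an estimate will ordinarily be read as a confidence limit, and the figure is too small even for an 80% interval. It needs correcting or labelling on either reading.

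A reader might go further and infer that d = 0.7 and AUC 0.75 contradict each other. The SAP does not support that:

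- It does not say what d measures, and it does not derive 0.75 from d.
- It attaches 0.75 to the logistic regression model. If that model holds several predictors, its AUC can exceed that of one predictor with d = 0.7.
- One value is used for power and the other for precision, and a plan may use different values for the two.
- The pilot cannot tell 0.69 from 0.75. With an assumed 3 versus 3, the 95% interval for d = 0.7 runs from about −1.0 to 2.3, which is an AUC of 0.24 to 0.95.

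The conversion also depends on its assumptions. If d were scaled by one group's SD, an SD ratio of 0.25 to 2 between the groups would give AUCs from 0.75 down to 0.62.

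Two smaller inferences also fail. N = 66 does not point uniquely to 33/33 two-sided, because a one-sided t-test with an 18/48 split has 80.5% power. Nor does 0.065 reveal a hidden planning AUC of 0.69: it matches the SE at AUC 0.69 with 33/33 (0.0652), but also the SE at AUC 0.75 with 25/41 (0.0648).

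None of this affects the precision result, which uses only the SAP's own N and AUC and an assumed event split.

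**Conclusion.** The precision statement is wrong as a reader would take it. At N = 66 and AUC 0.75 the 95% half-width is about 0.12 at the most favourable split and about 0.14 at 20/46, roughly twice the stated 0.065. This rests on the Hanley-McNeil approximation and an assumed event split; moving away from 50:50 towards fewer events makes the interval wider.

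The relation between d and AUC is a lack of reconciliation and not a demonstrated contradiction. It becomes a numerical mismatch (0.69 against 0.75) only if both values describe the single primary predictor, roughly normal with equal variances. If the 0.75 belongs to a joint model instead, the precision statement does not address the primary endpoint, and that would need saying.

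The wording that credits an assumed AUC with demonstrating good discrimination is unsound on any reading, but it is an editorial matter.

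**What to change.** In the SAP, Sample Size and Power Calculations:

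1. Replace ±0.065 with the 95% half-width and the assumed number of events: about ±0.12 to ±0.14 at AUC 0.75 for splits from 33/33 to 20/46, or about ±0.13 to ±0.15 at AUC 0.69. Name the method.
2. State which variable and which two groups d = 0.7 refers to, and the sidedness of the test.
3. State which model and predictor the planning AUC belongs to. If it is change in PPV with TVC, either use the AUC implied by d (about 0.69, with its assumptions) or give a separate justification for 0.75 and say that it is not the pilot effect.
4. Delete the phrase about demonstrating good discriminative ability and call the AUC an assumed value.

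The cost is wording and a less favourable stated precision. Enrolment, endpoint and analysis are unchanged. The 216 patients calculated above show the size of the gap and are not a proposed target.
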